To determine the feasibility of initiating a continuous glucose monitoring in patients with diabetes at hospital discharge. We hypothesize that starting and continuing to use a CGM at this critical time is feasible. Feasibility is defined as at least 20% of patients with diabetes referred for diabetes education meet inclusion criteria to participate and 75% agree to

participate. From those who participate, at least 50% continue using the CGM at 3 months.

B2 Secondary Aims

1. To characterize the barriers to continuing CGM use after discharge. We will systematically characterize the reasons for discontinuations (issues with wearing device, use, costs, getting refills, etc.)
2. To assess the effect of CGM initiation at hospital discharge on diabetes outcomes: Time in range, health utilization (clinic visits, ED visits, hospitalization), self-efficacy.

C Study Design

C1 Overview or Design Summary

This study will be an interventional, single-arm, open-label, prospective design.

C2 Subject Selection and Withdrawal

One hundred eligible adult patients will be recruited to the study.

2.a Inclusion Criteria

1. 18 years of age or older
2. Have diabetes (type 1 diabetes mellitus, type 2 diabetes mellitus, cystic fibrosis related diabetes mellitus)
3. Hemoglobin A1c greater than or equal to 8.0% or history of hypoglycemia unawareness
4. Able and willing to sign informed consent form
5. Have a valid telephone number
6. Willing to purchase FreeStyle Libre 2 CGM sensors out of pocket after discharge from hospital

2.b Exclusion Criteria

1. Unable to sign informed consent form
2. Have altered mental status
3. Unable to manage diabetes independently at home
4. Have utilized CGM in the past
5. Pregnancy
6. New steroid-induced hyperglycemia
7. Unwilling to participate in the study
8. Have kidney disease requiring hemodialysis
9. Taking high doses of vitamin C daily (greater than 500 mg every day)

2.c Subject Recruitment Plans and Consent Process

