The study team will identify potential participants from patients referred to the diabetes service or diabetes education service. Once a potential patient has been identified, one of the study team members will review the inclusion/exclusion criteria to determine if the patient is eligible to participate.

D2 Schedule of Measurements

VISIT/PHONE CALL (estimated time window)	WHAT WILL HAPPEN?
Screening Visit (~45 minutes)	Review consent form and obtain consent Complete questionnaire, obtain diabetes history
Day of Discharge (~1 hour)	Complete FreeStyle Libre 2 CGM education Attach FreeStyle Libre 2 CGM sensor to your arm
Within 1-3 weeks from discharge Phone Call (~30 minutes)	Questions regarding use of FreeStyle Libre 2 CGM Current diabetes regimen Adverse Events Reminder to take FreeStyle Libre 2 CGM sensor prescription to pharmacy to be filled
1 & 3 Month Phone Call (~45 minutes) [+/- 5 days]	Questions regarding use of FreeStyle Libre 2 CGM Current diabetes regimen Complete questionnaire Adverse Events
6 Month Phone Call (~15 minutes) [+/- 10 days]	Questions regarding use of FreeStyle Libre 2 CGM Barriers to FreeStyle Libre 2 CGM use

D3 Visit 1a: During Hospital Stay

Study team member will meet with participant, review informed consent form and obtain written consent. Study team member will obtain the following information from patient or medical record after consent is obtained:

1. Most recent A1c

- 2. Height/Weight; calculate body mass index (BMI)
- 3. Year of diagnosis with diabetes
- 4. Type of diabetes
- 5. Has patient been admitted to the hospital or emergency department in the past 3 months for a diabetes related problem
- 6. Home diabetes regimen
- 7. Hospital diabetes regimen
- 8. Hospital discharge treatment regimen
- 9. Participant's reason/goal for using FreeStyle Libre 2 CGM
- 10. Does participant have frequent hypoglycemia or hypoglycemia unawareness
- 11. Complete "Diabetes Self-Management Questionnaire"

D4 Visit 1b: Day of Hospital Discharge:

On the day of participant's discharge from the hospital, one of the diabetes educators will complete the following with the participant:

- 1. Teach participant how to set up the FreeStyle Libre 2 CGM
- 2. Teach participant how to attach the FreeStyle Libre 2 CGM sensor to the upper arm
- 3. Teach participant how to measure blood glucose with FreeStyle Libre 2 CGM reader or personal smart phone
- 4. Assist participant download the free FreeStyle Libre 2 app from the app store on smart phone

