- 5. Teach participant how to trouble shoot the FreeStyle Libre 2 CGM system
- 6. Provide participant with a handout for FreeStyle Libre 2 CGM system

The study physicians or nurse practitioners will provide the participant with a written prescription for three months of the FreeStyle Libre 2 CGM sensors to be filled by participant at their local pharmacy.

D5 Follow Up Telephone Calls

Within 1-3 Weeks after Discharge:

The study team will contact the participant by telephone to obtain the following information:

- 1. Is the participant still utilizing the FreeStyle Libre 2 CGM? If not, why was it stopped?
- 2. What barriers (such as discomfort, behavior modifications, lifestyle changes, diet changes) did the participant have with the FreeStyle Libre 2 CGM to limit use?
- 3. How satisfied with the FreeStyle Libre 2 CGM is the participant?
- 4. Has the participant been admitted to the hospital or been in the emergency department for a diabetes related problem since discharge?
- 5. Has the participant seen their outpatient diabetes provider since discharge?
- 6. What is the participant's current diabetes treatment regimen?

7. The study team will contact the participant to remind them to fill the prescription for a new FreeStyle Libre 2 CGM sensor with local pharmacy.

One Month after Discharge (+/- 5 days):

The study team will contact the participant by telephone to obtain the following information:

1. Is the participant still utilizing the FreeStyle Libre 2 CGM? If not, why was it stopped?
2. What is the average blood glucose for the past 30 days?
3. What barriers (such as discomfort, behavior modifications, lifestyle changes, diet changes) did the participant have with the FreeStyle Libre 2 CGM to limit use?
4. How satisfied with the FreeStyle Libre 2 CGM is the participant?
5. Has the participant been admitted to the hospital or been in the emergency department for a diabetes related problem since discharge?
6. Has the participant seen their outpatient diabetes provider since discharge?
7. What is the participant's current diabetes treatment regimen?
8. Administer the Diabetes Self-Management Questionnaire

Three Months after Discharge (+/- 5 days):

The study team will contact the participant by telephone to obtain the following information:

1. Is the participant still utilizing the FreeStyle Libre 2 CGM? If not, why was it stopped?
2. What is the average blood glucose for the past 30 days?

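### ED visits and hospitalizations share one uncounted item, and the baseline look-back does not exclude the index stay, so a before/after comparison could show an artificial fall

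*Combined protocol and SAP*

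**What the plan says.** Secondary Aim 2 in section B2 sets out to assess the effect of starting the device at discharge on "Time in range, health utilization (clinic visits, ED visits, hospitalization), self-efficacy". Utilization therefore has three named components.

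Section D5 collects them with two questions, asked at the 1-3 week, 1-month and 3-month calls:

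- Hospital and ED together: "Has the participant been admitted to the hospital or been in the emergency department for a diabetes related problem since discharge"
- Clinic contact: "Has the participant seen their outpatient diabetes provider since discharge"

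Neither question asks for a number or a date, and both run cumulatively from discharge. The 6-month call has no utilization item.

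The baseline information comes under "D3 Visit 1a: During Hospital Stay", where item 5 reads "Has patient been admitted to the hospital or emergency department in the past 3 months for a diabetes related problem". The list has no baseline question on clinic visits. The baseline source is the patient or the medical record; the follow-up source is the telephone call.

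Section F2 provides for descriptive statistics, and for a pre/post ANOVA of the questionnaire only. Section C1 describes a single-arm design.

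**The concern.** There are two separate problems.

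The first is what can be reported. Aim 2 lists ED visits and hospitalization as different outcomes, but a yes to the joined question does not say which occurred, or how often. One ED visit and four admissions give the same answer. Nothing else in the listed data separates them.

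The second is the baseline. The item is asked while the participant is in hospital, and its 3-month look-back includes the current stay. If that stay is for a diabetes-related problem, it satisfies the item as worded. The follow-up window starts at discharge and cannot include it. With no control arm, the participant's own baseline is the only comparator inside the study for an effect on utilization. If it is inflated, the device could be credited with a fall that comes from the wording of the question.

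**Working it through.** The documents give no utilization rate, effect size or power figure, so there is nothing to reproduce. The check has two parts.

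**Aim against data items**

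| Component in Aim 2 | Baseline (D3) | Follow-up to 3 months (D5) | What can be reported |
|---|---|---|---|
| Clinic visits | no item | own item, diabetes provider only, no count | any contact since discharge; no before/after |
| ED visits | joined with hospital | joined with hospital, no count | not separable |
| Hospitalization | joined with ED | joined with ED, no count | not separable |

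This part rests on the text alone.

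**Size of a possible artificial fall**

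Inputs, both assumed because the documents give neither:

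- b: the true 3-month probability of a diabetes-related admission or ED visit, apart from the index stay. It is taken as equal before and after, so there is no device effect. Range 5% to 30%.
- q: the share of participants whose index stay is recorded as a yes at baseline, taken as independent of other events. Values 0%, 10%, 25% and 50%.

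Formulas:

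- Baseline yes = b + q(1 − b)
- Yes at the 3-month call = b
- Artificial fall = q(1 − b)

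Results:

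| q | Fall at b = 5% | Fall at b = 30% |
|---|---|---|
| 0% | 0 | 0 |
| 10% | 0.10 × 0.95 = 9.5 points | 0.10 × 0.70 = 7.0 points |
| 25% | 0.25 × 0.95 = 23.8 points | 0.25 × 0.70 = 17.5 points |
| 50% | 0.50 × 0.95 = 47.5 points | 0.50 × 0.70 = 35.0 points |

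One case in full, with b = 10% and q = 25%: baseline yes = 0.10 + 0.25 × 0.90 = 32.5%, against 10% at 3 months, a fall of 22.5 points. If someone tested this with an exact two-sided McNemar test at an assumed 5% level, with independent answers, it would be called significant 73% of the time with 50 participants and 97% with 100. With q = 0 the corresponding rates are 2% and 3%. The two sample sizes are used because section F1 can be read as 100 enrolled, or as 100 approached with half agreeing.

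**Window length**

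Only the 3-month call covers about the same length of time as the baseline. Answers at 1-3 weeks and 1 month cover less time, so comparing them with baseline would also push towards a fall.

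**The case against.** Three points can fairly be made for the plan.

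- F2 plans no pre/post test of utilization, and the baseline item sits in a history list without being called a utilization baseline. This stands: the bias does harm only if baseline and follow-up are compared. But Aim 2 speaks of an effect, and a single-arm study has no other internal comparator.
- Baseline data may come from the medical record, so staff might leave out the index stay. They might, but nothing tells them to.
- This is one element of a secondary aim, and the primary feasibility criteria are untouched. This also stands.

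A reader might also infer more than the documents support:

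- *That none of the three outcomes can be separated.* Clinic contact has its own item at all three calls; only ED visits and hospitalization are merged.
- *That a fall is certain because everyone enrolled is in hospital.* The baseline item is limited to diabetes-related problems. Eligibility in section C2 does not require a diabetes-related admission, and the background section describes diabetes as a comorbidity of inpatients. The fall arises only where the index stay is diabetes-related and is counted.
- *That overlapping follow-up windows make the answers useless.* The cumulative answer at 3 months is a valid ever/never measure of the joined outcome. Overlap matters only if answers are to be added up.

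**Conclusion.** The concern holds in two parts of different strength. From the text alone, ED visits and hospitalizations cannot be reported separately or counted as collected, and clinic contact has no baseline. The second part is conditional: the baseline wording allows the index stay to be counted, and a before/after comparison could then show a fall with no device effect. Its size depends mainly on q, and the figures in the working are illustrations, not bounds. Recruitment through the diabetes and diabetes education services, with a raised A1c or hypoglycemia unawareness required, makes some diabetes-related index stays plausible, but the documents give no share. The documents do not support saying that a large fall is bound to appear. The point is worth acting on because the change is small and has to precede data collection: counts and event types cannot be reliably rebuilt from recall later.

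**What to change.** 1. Word the baseline item to cover the 3 months before this admission, not counting this admission.
2. At baseline and at follow-up, record ED visits, hospitalizations and outpatient diabetes-provider visits as three separate counts.
3. Choose one follow-up window rule. Either ask since discharge at every call and use the cumulative 3-month answer, or ask since the last call at all three calls, including the 1-3 week call, and sum them. If counts since the last call were taken only at 1 and 3 months, events before the 1-3 week call would be lost, which would itself create a fall.
4. State in F2 that utilization is summarized descriptively, and that only the 0-3 month total is compared with the 3-month baseline.

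The cost is one added baseline question on clinic visits, slightly longer calls, and reliance on participants' recall of counts instead of a yes or no. No new contact is needed.

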Diabetes is a very common comorbidity in hospitalized patients. Patients with diabetes are highly likely to be hospitalized, with insulin use increasing this likelihood (1). It is estimated that up to 38% of patients in the hospital have diabetes or hyperglycemia, and likely many more have pre diabetes (2). Diabetes is associated with worse hospital outcomes including increased risk for falls, infections and readmissions. The hospital stay represents an opportunity to intervene and optimize diabetes management. Patients at our hospital also have access to specialized services including endocrinologists and certified diabetes educators. However, diabetes is a complex disease and is common for patients to feel overwhelmed with the burden of therapy. Continuous glucose monitors (GCMs) are commercially FDA approved devices for single-patient use that can measure interstitial glucose every 5 minutes. They vary slightly in the number of wear days, display and need of calibrations. Studies have shown that CGM use improves diabetes control and decrease episodes of hypoglycemia (3-5). One barrier for the effectiveness is uptake, they are not prescribed enough by primary care providers, another significant barrier has been cost. The overall goal of this current study is to assess the feasibility of initiating CGM in patients with diabetes at discharge. This strategy has the potential to overcome delay in accessing the technology and control cost.

One study looked at the feasibility of use in older patients with diabetes and dementia in the outpatient setting. In this study, of 17 people consented and 12 completed the study. Patient and caregivers reported that the device was nonintrusive and responded positively about recommending the device (6). Another study in the outpatient setting found that a total of 22 participants (48.9%) completed the study using the minimum number of 3 FreeStyle Libre sensors with 11 of the participants requiring extra sensors due to a faulty or misplaced sensor (7). One study using a 4 month Telehealth outpatient model utilizing CGM, showed 92% (55/60) completed the 4-month intervention, and 78.2% (43/55) met the criteria of follow-up CGM sensor-wear periods >90 days from baseline. This study showed improved time in range and a decrease in A1C by 1.6% (8).

B Study Objectives

B1 Primary Aim

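### Aim 2 names clinic visits, but the calls ask only about the participant's own diabetes provider, so diabetes visits elsewhere may be missed and a negative answer is ambiguous

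*Combined protocol and SAP*

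**What the plan says.** The second secondary aim (section B2, item 2) is "To assess the effect of CGM initiation at hospital discharge on diabetes outcomes", and the outcomes listed under it are "Time in range, health utilization (clinic visits, ED visits, hospitalization), self-efficacy". Clinic visits are not defined further, either by type of clinician or by reason for the visit.

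Section D5 collects utilization by telephone. At the 1-3 week call (item 5), the one-month call (item 6) and the three-month call (item 6), the outpatient question is "Has the participant seen their outpatient diabetes provider since discharge". The companion hospital question at the same calls is "Has the participant been admitted to the hospital or been in the emergency department for a diabetes related problem since discharge". The six-month call has no utilization question.

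At baseline, section D3 item 5 asks "Has patient been admitted to the hospital or emergency department in the past 3 months for a diabetes related problem". None of the 11 baseline items asks about clinic visits or about having an outpatient diabetes provider. Section F2 gives descriptive statistics and an ANOVA for the questionnaire, with no rule for turning the call answers into a clinic-visit outcome.

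**The concern.** The aim and the question mark out different sets of events. The aim speaks of visits to clinics. The question speaks of one clinician, identified by the participant's own view of who that is. Someone seen for diabetes in primary care after discharge has had a clinic visit, but may answer no. Someone with no diabetes provider has no response that fits.

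At stake is one of the three named utilization components of a secondary aim. A reader who sees the percentage of affirmative answers reported as clinic visits could not tell whether the remainder went without outpatient care, received it elsewhere, or had no provider of the kind asked about. The plan describes no way to separate these later.

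**Working it through.** The plan states no figure on this point, so the check compares the text.

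**1. How each utilization item is limited.**

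| Component in B2 item 2 | Question in D5 | Limited by |
|---|---|---|
| ED visits, hospitalization | one combined item | reason (diabetes related) |
| Clinic visits | one item | clinician (own diabetes provider) |

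B2 places all three components under diabetes outcomes, so a limit by reason is a fair reading for all of them. The ED and hospital item follows that limit. The clinic item uses a different one.

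**2. Whether the two limits coincide.** They do so only if every diabetes-related clinic visit is to a clinician the participant calls their diabetes provider, and every visit to that clinician concerns diabetes. Nothing in the plan secures either condition. No inclusion criterion in C2 requires an outpatient diabetes provider. Recruitment is from patients referred to the diabetes or diabetes education service, and such a referral does not show that the patient has a provider outside the hospital.

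**3. Whether another source fills the gap.** The medical record is named as a source at the baseline visit ("Study team member will obtain the following information from patient or medical record after consent is obtained"), but not at the calls. The remaining call items cover device use, barriers, satisfaction, treatment regimen and the questionnaire, and the D2 schedule adds adverse events. None records outpatient visits.

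**4. What a negative answer can mean.** (a) No outpatient visit for diabetes; (b) a visit for diabetes to a clinician not regarded as the diabetes provider; (c) no such provider. States (b) and (c) can occur together. One yes/no answer cannot distinguish them.

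**5. Size.** Let p be the share of participants with any diabetes-related clinic visit by 3 months, and q the share of those seen only by clinicians they do not count as their diabetes provider. If the question is taken literally and only this loss operates, the reported share is p(1 - q). The documents give neither value. As an illustration only, assume p = 0.70:

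- q = 0: 0.70 × 1.00 = 70%, no shortfall
- q = 0.10: 0.70 × 0.90 = 63%, 7 points short
- q = 0.20: 0.70 × 0.80 = 56%, 14 points short
- q = 0.40: 0.70 × 0.60 = 42%, 28 points short

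These results restate the assumptions and do not estimate the error in this trial.

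**The case against.** The strongest reply is that the plan is coherent as it stands. Health utilization sits under diabetes outcomes, the ED and hospital question is confined to diabetes-related problems, and asking about the diabetes provider keeps to the same theme. On that reading, a visit to an unrelated clinic is rightly left out. The word provider is also not reserved for specialists: the background section itself uses it for primary care ("they are not prescribed enough by primary care providers"). A primary care clinician who manages the diabetes could therefore be the provider meant, and staff on the telephone can clarify.

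Much of this stands. A diabetes-only scope is plausible, and all-cause clinic visits should not be assumed to be the target. The background remark concerns CGM prescribing and says nothing about who sees these participants after discharge. The mismatch nevertheless survives the diabetes-only reading, because the clinic question limits by clinician and not by reason. Whether primary care counts is left to each participant or caller, as the term is undefined and no script is described.

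A reader might go further and infer three things that the documents do not support:

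- *Visits elsewhere are scored as no visit.* No scoring rule exists. Such visits are not captured, and draw a negative answer only if the question is taken literally.
- *Participants without a diabetes provider can never answer yes.* They may count a primary care clinician, or acquire a provider before a later call.
- *The result is biased downward by a known amount.* The size rests wholly on assumed rates. The net direction is not settled either: if primary care is counted, a visit there for another reason could draw a yes.

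It is also true that, with a single arm and no baseline clinic-visit item, no wording of this question would allow an effect on clinic visits to be estimated. What can be improved is the description of outpatient use after discharge.

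**Conclusion.** The point holds as a minor mismatch between a stated outcome and the item that collects it. The plan names clinic visits but records only whether the participant has seen a clinician they regard as their diabetes provider. A negative answer has several meanings that nothing else in the plan separates. If the answers are reported as clinic visits, outpatient use may be understated.

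This rests on two assumptions: that the question is taken literally, and that some participants are seen for diabetes only by clinicians they do not call their diabetes provider. If participants count primary care, the loss may be nil. Only one component of a secondary aim is affected. No planned test or threshold depends on it, and the B1 criteria are untouched.

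**What to change.** Preferred: reword the outpatient item at the 1-3 week, one-month and three-month calls along these lines: *Since discharge, has the participant had an outpatient clinic visit for diabetes? If yes: (a) primary care, (b) endocrinology or diabetes clinic, (c) other.* Add a response for participants who have no outpatient diabetes provider. Report any diabetes-related clinic visit as the Aim 2 component, which matches the scope of the ED and hospital item, and give category (b) on a separate line.

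Alternative: if only visits to a diabetes provider are of interest, narrow B2 item 2 to say so. Add a yes/no item to the D3 baseline list on whether the participant has such a provider, so that those without one are reported separately.

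Either needs a minor protocol amendment. The preferred version adds a few seconds per call and brings some misclassification, since participants report the type of clinic themselves. Answers already collected under the present wording cannot be reclassified from the data the plan collects and should be reported under the question actually asked.

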The study team will identify potential participants from patients referred to the diabetes service or diabetes education service. Once a participant is identified, one of the study team members will approach the patient in their private hospital room, review the study and provide them with a written informed consent form to review. The study team will follow up 1-2 days later or prior to discharge to determine if the patient is interested in participating. If the patient is interested, the study team will review the informed consent form with them, answer all study related questions and obtain written informed consent. If a patient is not interested in the study, the study team will not coerce them into participating; participation is completely voluntary.

2.d. Risks and Benefits

Participants may or may not benefit from participating in the study. Benefits of participating in the study may include the following:

1. Improved understanding of diabetes
2. Improved ability to manage diabetes
3. Discover glucose patterns previously unaware of.

Potential risks of participating in the study include the following:

1. Improperly treated diabetes risks may include: hypoglycemia, hyperglycemia, or ketoacidosis.
2. CGM sensor insertion risks may include: feeling like insulin injection; tenderness at the sensor site.
3. Pain, redness, swelling, minor infection and minor bleeding at the sensor insertion site.
4. Redness may occur where the device adhesive pads are placed.
5. Allergic reaction to one of more parts of the sensor.
6. Skin may blister or peal at the site of the sensor.
7. Sensor or insertion needle may break.
8. Fingerstick testing risks may include: finger feel sore, tender or may bleed.
9. Questionnaire risks may include: some questions may cause the participant to feel uncomfortable.

2.e. Early Withdrawal of Subjects

Participants may be withdrawn if certain situations arise:

1. Participant does not follow study instructions
2. Change in participant's medical condition (i.e., pregnancy, worsening clinical condition)
3. The study team or government agencies stop the study
4. In the opinion of the study team, there is no value in participant continuing the study.

5. If new information becomes available or harmful unexpected reactions are experienced by participants in the study.

C3 Study Device

3.a Description

FreeStyle Libre 2 Continuous Glucose Monitoring System manufactured by Abbott

D Study Procedures

D1 Screening for Eligibility

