3. What barriers (such as discomfort, behavior modifications, lifestyle changes, diet changes) did the participant have with the FreeStyle Libre 2 CGM to limit use?
4. How satisfied with the FreeStyle Libre 2 CGM is the participant?
5. Has the participant been admitted to the hospital or been in the emergency department for a diabetes related problem since discharge?
6. Has the participant seen their outpatient diabetes provider since discharge?
7. What is the participant's current diabetes treatment regimen?
8. Administer the Diabetes Self-Management Questionnaire

Six Months after Discharge (+/- 10 days):

The study team will contact the participant by telephone to obtain the following information:

1. Is the participant still utilizing the FreeStyle Libre 2 CGM? If not, why was it stopped?

2. What barriers (such as discomfort, behavior modifications, lifestyle changes, diet changes) did the participant have with the FreeStyle Libre 2 CGM to limit use?

E Safety Monitoring

E1 Safety and Compliance Monitoring

The study team will meet every other week to review the status of the study, progress of recruitment, and adverse events. The study team will communicate directly with one another in between scheduled study team meetings if an unexpected adverse event occurs.

E2 Medical Monitoring

The study team will monitor patients throughout their participation in the study. Any adverse event or unexpected adverse event will be brought to the principal investigator within 24 hours of study team notification of event.

F Statistical Plan

F1 Sample Size Determination and Power

One hundred patients will be recruited for the study with the anticipation that 50% will agree to participate in the study.

F2 Statistical Methods

Statistical methods will include descriptive statistics (means, SD, median, IQR) and pre-test/post-test ANOVA for the questionnaire.

G References

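### F1 anticipates 50% agreement while B1 requires 75%, with no stated common denominator; what the 100 patients count, and whether refusers count as ineligible, are left open

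*Combined protocol and SAP*

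**What the plan says.** **Agreement.** Section B1 sets three conditions for feasibility. At least 20% of patients referred for diabetes education must "meet inclusion criteria to participate and 75% agree to" take part, and a third condition follows: "From those who participate, at least 50% continue using the CGM at 3 months". B1 also states the expectation of success: "We hypothesize that starting and continuing to use a CGM at this critical time is feasible". Section F1 consists of one sentence: "One hundred patients will be recruited for the study with the anticipation that 50% will agree to participate in the study". It gives no power, precision target or denominator.

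**Size.** Section C2 says: "One hundred eligible adult patients will be recruited to the study".

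**Eligibility and consent.** Inclusion 4 in section 2.a is "Able and willing to sign informed consent form". Exclusion 7 in section 2.b is "Unwilling to participate in the study". Inclusion 6 requires willingness to pay for sensors after discharge. Section 2.c places the decision after the approach in hospital: "The study team will follow up 1-2 days later or prior to discharge to determine if the patient is interested in participating". Section D1 has a team member check the criteria once a potential patient is identified. Neither 2.c nor D1 refers to the other.

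**The concern.** Three things about the primary aim cannot be settled from the text.

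1. F1 expects an agreement rate 25 points below the one B1 requires, in nearly the same words, and no section says whether the two rates share a denominator.
2. The number of participants is not fixed. C2 taken alone suggests 100 people wearing the device; F1 suggests 100 people asked and about half that number wearing it.
3. Willingness to take part is itself an eligibility criterion, so the same refusal can be charged either to B1's 20% or to its 75%.

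The third item has the most direct effect on the conclusion. If the counting rule is chosen after the data are in, the same patients can pass one criterion and fail the other, or the reverse. The second item governs how precisely 3-month continuation is estimated and how many patients must be approached.

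**Working it through.** **Can 100 be reproduced?** No. F1 states no alpha, power, precision target or dropout rate, so there is no calculation to repeat.

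**Step 1: what 100 implies.** Inputs: 100 (F1, C2), 50% (F1), 75% (B1). Enrolled = approached × rate; approached = enrolled ÷ rate, rounded up.

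| Meaning of 100 | At 50% agreement | At 75% agreement |
|---|---|---|
| Approached | 100 × 0.50 = 50 enrolled | 100 × 0.75 = 75 enrolled |
| Consented | 100 ÷ 0.50 = 200 approached | 100 ÷ 0.75 = 133.3, so 134 approached |

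The figure of 50 enrolled is derived; the plan does not state it.

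**Step 2: precision for 3-month continuation.** Exact (Clopper-Pearson) 95% interval for x of n: lower limit = 0.025 quantile of Beta(x, n − x + 1); upper limit = 0.975 quantile of Beta(x + 1, n − x). The observed proportion is set near B1's 50%.

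| N | x | 95% CI |
|---|---|---|
| 50 | 25 | 35.5% to 64.5% |
| 75 | 38 | 38.9% to 62.4% |
| 100 | 50 | 39.8% to 60.2% |

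B1's rule is an observed proportion of at least 50%, that is, at least 25 of 50, 38 of 75 or 50 of 100. The true rates of 40% and 60% below are illustrative assumptions; the plan gives none.

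| True continuation | N = 50 | N = 75 | N = 100 |
|---|---|---|---|
| 60%: chance of passing | 0.943 | 0.960 | 0.983 |
| 40%: chance of passing | 0.098 | 0.040 | 0.027 |

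N therefore matters mainly for precision and for the chance of a false pass.

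**Step 3: how refusals are counted.** Take 500 referred patients, of whom 100 meet every criterion other than willingness (100 ÷ 500 = 20%, B1's floor). Let 50 or 75 of them consent.

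| Counting rule | Consenting | Eligibility rate (B1: 20%) | Agreement rate (B1: 75%) |
|---|---|---|---|
| Refusal = non-agreement | 50 | 100/500 = 20% | 50/100 = 50% |
| Refusal = ineligible | 50 | 50/500 = 10% | 50/50 = 100% |
| Refusal = non-agreement | 75 | 100/500 = 20% | 75/100 = 75% |
| Refusal = ineligible | 75 | 75/500 = 15% | 75/75 = 100% |

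Under the literal reading of inclusion 4 and exclusion 7, agreement is close to 100% whatever patients decide, and the eligibility rate absorbs the refusals. A patient who declines only because of sensor cost raises the same question through inclusion 6.

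**The case against.** **A forecast is not a threshold.** A cautious recruitment assumption can sit below a success criterion without contradicting it. This stands. B1 remains the decision rule, and F1's 50% does not alter how an observed rate is judged.

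**The denominators may differ.** F1 speaks of patients, not eligible patients. If, purely as an illustration, two thirds of those approached qualified, 75% agreement among them would be 2/3 × 0.75 = 50% of those approached, and the figures would be compatible. C2's reference to eligible patients counts against this reading but does not exclude it. Nor do D1 and 2.c fix an order between checking criteria and approaching the patient; willingness to consent or to pay can hardly be known before asking. So the two rates cannot be called directly opposed. What stands against the plan is that it states no denominator.

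**C2 can be harmonised with F1.** Both use the same number and verb, and F1's agreement rate points to 100 approached. This is a fair reading, but C2 on its own reads as 100 enrolled and nothing in the text decides between them.

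**The effect is modest.** For continuation this is largely true: at a true 60% the rule passes with probability 0.94 or more at any of the three sizes. It is not true of the counting of refusals, which can move a primary criterion from failing to met.

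**Conclusion.** The point holds as a matter of unreconciled figures and an undefined denominator, and it should be fixed. F1's 50% and B1's 75% are unrelated in the text. Enrolment is about 50 or 100 depending on whether F1 or C2 is followed. Inclusion 4 and exclusion 7, read literally, make the 75% criterion nearly automatic while lowering the eligibility rate.

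Two stronger inferences should be resisted. A reader might conclude that the study is planned to miss its own criterion. If 50% were the true rate among 100 eligible patients approached, the chance of seeing at least 75 agree would indeed be below 0.0001; but that treats a one-line expectation as the truth, on a denominator that F1 does not give. A reader might also guess that F1's 50% was copied from B1's continuation criterion; nothing in the text supports that.

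The sizes quoted rest on F1's and B1's rates taken at face value, on continuation near 50%, and, for the refusal example, on eligibility at B1's 20% floor.

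**What to change.** 1. In F1 and C2, state whether 100 counts patients approached or patients who consent, and give the corresponding other number from the first table above.
2. In B1, define the denominator of the 75% as patients approached who meet the criteria other than willingness to consent or participate, so that a refusal is non-agreement and not ineligibility under inclusion 4 or exclusion 7. State whether unwillingness to buy sensors (inclusion 6) counts against the 20% or the 75%.
3. In F1, give the anticipated agreement rate on that denominator. Either align it with 75% or say that the expected rate is below the criterion. Then state the expected N for 3-month continuation and its exact 95% interval.

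The cost is a few sentences in B1, C2 and F1. B1's thresholds stay as they are, and no patients are needed beyond the number the team intended. The downside is that the stated expectation or precision may look less favourable.
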